In the only previous study with a similar design to the SUPER-Fin trial, [20] 40% of 40 patients in the non-surgical group reported had "compromised fracture healing": namely, eight fracture displacements and eight with a delayed or non-union. However, only two of these patients required secondary surgery. In the surgery arm, in turn, six patients experienced a post-operative wound infection, but only one required a secondary surgery to revise the wound. In addition, there were four patients treated initially with surgery that required a secondary surgery to remove a symptomatic hardware.

Although data on the exact incidences and long-term effects of downsides/adverse consequences of both treatment strategies is scarce, it seems highly likely that our analysis will be underpowered. Furthermore, both treatment strategies have unique, characteristic adverse consequences that would likely unblind the treatment given for outcome assessors and/or those interpreting the data.

For the above noted reasons, particularly to preserve blinding, we have decided to only assess the incidence of secondary surgery in both groups in our primary efficacy analysis, as we consider this outcome to be most appropriate (blinding-preserving) for comparing the major downsides of the two treatment strategies. However, to be completely transparent and inclusive about the possible effect of adverse consequences on the clinical relevance (interpretation) of our findings, we commit to also considering the rate of non-unions before finalising our interpretation. However, this more comprehensive analysis on the downsides of the two treatments will not change our assessment on efficacy, rather possibly only change the wording of a possible notion on adverse consequences, and accordingly, it will be carried out after we have reached a consensus on efficacy (and unblinded the treatment assignment = broken the randomization code).

The sequence of events to take place in the upcoming "blinded data interpretation meeting" is outlined in the flow chart below:

[figure not shown]

1. Analysis on efficacy (primary, non-inferiority): Is non-surgical treatment non-inferior to surgery?

Table 1. Baseline characteristics.

	Group A	Group B
Characteristic	(n = ??)	(n = ??)
Age at fracture years, mean (SD) [range]		
Patients aged over 50 years, No. (%)		
Gender, No. (%)		
Men		
Women		
Level of education*, No. (%)		
Basic education (ISCED 2)		
Upper secondary education (ISCED 3-4)		
Short-cycle tertiary education (ISCED 5)		
Bachelor, Master or Doctoral (ISCED 6–8)		
Did not wish to answer or missing		
Place of occurrence (ICD-10) †, No. (%)		
Leisure activity		
Working for income		
Sports activity		
Other		

Figure 1. Trial flowchart (participant numbers to the point of randomization – not beyond, to preserve blinding)

ITT, intention-to-treat; ER, external rotation; OMAS, Olerud-Molander Ankle Outcome Score.

Table 2. Primary outcome at the primary outcome assessment time point (24 months).^a

	Group A		Group B		Difference (95% CI)
	n	Mean \pm SD	n	Mean ± SD	
Primary efficacy outcome					
OMAS (Scale: 0 to 100)	TBA*	?? + ??	TBA*	?? ± ??	?? ± ??

^{*} TBA (to be added, later): To preserve blinding, n-values for Groups A and B will only be added after randomization code is broken.

Our judgment on the efficacy (non-inferiority) will be based on the location of the whole CI in relation to Δ (non-inferiority margin), as outlined by Piaggio et al².

SUPER-Fin / Generic NEW TREATMENT BETTER NEW TREATMENT WORSE Superior A Noninferior В Noninferior Noninferior? D Inconclusive E Inconclusive Inconclusive? G Inferior H Treatment difference for adverse outcome (new treatment minus reference treatment)

As we will not have knowledge of treatment group assignment (whether Group A or Group B is our "new treatment": here, non-surgical treatment), and to preserve our blinding, we have deemed it necessary to take both scenarios under consideration, as follows:

- We will calculate the treatment group difference assuming first that Group A is the "new treatment" and then that Group B is the "new treatment" (Scenario 1 and Scenario 2).
- We will plot the resulting point estimate with error bars (95% Cis) into two separate graphs.
- We will interpret both graphs (Figures 2 and 3).

Figure 2. Scenario 1: Group A minus Group B.

(EXAMPLE GRAPH BELOW, to be replaced by the actual graph of the SUPER-Fin trial data).

[figure not shown]
[figure not shown]

Figure 3. Scenario 2: Group B minus Group A.

(EXAMPLE GRAPH BELOW, to be replaced by the actual graph of the SUPER-Fin trial data).

Initial interpretation:

Based on the location of the whole CI in relation to Δ (non-inferiority margin), our initial interpretation on the non-inferiority of non-surgical treatment (vs. surgery), is as follows:

Scenario 1 (Figure 2)

Group A is [superior A / non-inferior B to D / inferior H] to Group B in the treatment of ER-stress unstable Weber-B unimalleolar ankle fractures.

OR

Our results are inconclusive [to] regarding the non-inferiority of the two groups in the treatment of ER-stress unstable Weber-B unimalleolar ankle fractures.

Scenario 2 (Figure 3)

Group B is [superior A / non-inferior B to D / inferior H] to Group A in the treatment of ER-stress unstable Weber-B unimalleolar ankle fractures.

OR

Our results are inconclusive [to] regarding the non-inferiority of the two groups in the treatment of ER-stress unstable Weber-B unimalleolar ankle fractures.

2. Need for secondary surgery in the two treatment strategies?

	No.*			
	Group A	Group B	P-value	
Secondary surgery	?	?		

^{*} Given that the treatment groups should be quite balanced, we refrain from laying out the percentages and simply rely on crude n-values at this stage.

Imbalance between the two groups in the need for secondary surgery?

YES / NO

- If NO, our initial interpretation on efficacy (previous page) stands as is.
- If YES => We will add the following notion about the imbalance (excess in harms) to our interpretation:

[&]quot;However, there was a noteworthy imbalance in the need for secondary surgery between the two treatment strategies (higher/lower rate in Group A) and this should be considered when interpreting the trial findings."

3. Unblinding

After consideration of the major downsides of the two treatment groups, we have now reached a consensus on our blinded assessment on efficacy.

Our statistician will now unblind the treatment group assignment (break the randomization code):

Group A = Non-surgical treatment / Surgery [incorrect option to be removed]
Group B = Non-surgical treatment / Surgery [incorrect option to be removed]

Given the above noted, the SUPER-Fin data is shown in **Table 1** (with n-values for Groups to be added) and in Scenario 1 (**Figure 2**) or Scenario 2 (**Figure 3**). [incorrect option to be removed]

Table 2. Primary outcome at the primary outcome assessment time point (24 months).

	Group A		Group B		Difference (95% CI)
	n	Mean \pm SD	n	$Mean \pm SD$	
Primary efficacy outcome					
OMAS (Scale: 0 to 100)	TBA	?? + ??	TBA	?? + ??	?? + ??

4. Unblinded interpretation on efficacy after consideration of the need for secondary surgery in the two treatment strategies

Accordingly, our penultimate interpretation of the SUPER-Fin trial is as follows:

[incorrect options to be removed]

(1) Non-surgical treatment is superior to surgery in the treatment of ER-stress unstable Weber-B unimalleolar ankle fractures. However, be it noted that we did not set a superiority hypothesis in the study protocol.

OR

(2) Non-surgical treatment is non-inferior to surgery in the treatment of ER-stress unstable Weber-B unimalleolar ankle fractures.

OR

(3) Non-surgical treatment is inferior to surgery in the treatment of ER-stress unstable Weber-B unimalleolar ankle fractures.

OR

(4) Our results are inconclusive regarding the non-inferiority of the two groups in the treatment of ER-stress unstable Weber-B unimalleolar ankle fractures.

In addition to the primary conclusion above, the following notion regarding downsides of the two treatments will / will not be added [incorrect option to be removed] based on our assessment of the need for secondary surgery (Section 2):

"However, there was a noteworthy imbalance in the need for secondary surgery between the two treatment strategies (higher/lower rate in Group A) and this should be considered when interpreting the trial findings."

To finalise our interpretation, we will proceed into unblinded assessment of all downsides related to both treatments (Section 5., next page).

5. Consideration of non-unions (in addition to secondary surgery) of the two treatment strategies

	No. (%)		
	Group A	Group B	P-value
Non-union at 24 months			
Asymptomatic	? (?%)	? (?%)	.???
Symptomatic	? (?%)	? (?%)	
Secondary surgery	?	?	

We note that the rate of non-unions – if dramatically different – could theoretically tilt the previously observed (im)balance in the incidence/risk of downsides of the two treatment groups. For the sake of transparency, we commit to considering the rate of non-unions but maintain that if not symptomatic enough to require secondary surgery, their clinical relevance is limited and will only require possible slight modification to our cautionary tail.

Imbalance between the two groups in all treatment-related downsides? YES / NO

- If NO, our final interpretation on efficacy (previous page) stands as is.
- If YES => We will add the following notion about the imbalance (excess in harms) to our interpretation:

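### Secondary surgery is called blinding-preserving, but the plan's own prior data let counts by Group A and Group B support a better-than-chance guess at allocation before the code is broken

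*SAP*

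**What the plan says.** Under *Blinded data interpretation*, item 2 (safety concerns), the SAP argues that each strategy has harms peculiar to it, and that these would probably reveal the treatment to those interpreting the data. It therefore limits the blinded harms comparison to secondary surgery, "as we consider this outcome to be most appropriate (blinding-preserving) for comparing the major downsides of the two treatment strategies".

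Just before this, the SAP summarises the only earlier trial of similar design. Of the non-surgical patients with compromised healing, "only two of these patients required secondary surgery". In the surgery arm, "six patients experienced a post-operative wound infection, but only one required a secondary surgery to revise the wound", and in addition "there were four patients treated initially with surgery that required a secondary surgery to remove a symptomatic hardware".

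The meeting template then runs in this order:

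- **Section 1:** an initial non-inferiority reading from the OMAS confidence interval, written for both scenarios with closed-option sentences.
- **Section 2:** crude counts of secondary surgery for Group A and Group B with a P-value, then a YES / NO answer on whether there is an imbalance. NO leaves the initial reading as it is; YES adds one pre-written caution.
- **Section 3:** the statement "After consideration of the major downsides of the two treatment groups, we have now reached a consensus on our blinded assessment on efficacy", followed by breaking the code.
- **Section 4:** the penultimate interpretation, in which the same caution sentence appears again.

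**The concern.** The reason given for choosing this outcome is that it does not point to an arm. The plan's own evidence suggests that it may. The SAP describes the surgical arm as open reduction and plate fixation, and four of the five secondary operations it reports after surgery were removals of symptomatic hardware. That is the kind of arm-specific event the plan says it wants to keep out of view. The committee works from a document containing these figures and is then given the count for each coded group.

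The Section 2 answer has no threshold and rests wholly on judgement, so it is the step most open to influence from a guess about allocation. The Section 1 reading is called initial. Nothing in the text locks it before Section 2 is opened, and consensus is declared only in Section 3. The SAP takes other care here: it holds back the group sizes in Table 2 and the flowchart after randomisation. Crude counts of this outcome by group are out of step with that care.

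**Working it through.** **Inputs**

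- Non-surgical arm of the cited trial: 2 secondary operations in 40 patients, 2/40 = 5.0% (SAP).
- Surgery arm of the cited trial: 1 wound revision + 4 hardware removals = 5 (SAP). The size of this arm is not given. Assumed 40, so 5/40 = 12.5%; range 35 to 45, so 14.3% to 11.1%.
- Patients per arm in the present trial: 63 (SAP, *Sample size*), or about 50 after the planned 20% dropout (63 × 0.8 = 50.4). The 63 is used only as a number of patients.

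The plan gives no figure of its own for how well this outcome protects the blind, so there is none to reproduce.

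**Formula.** Let X_S and X_N be independent counts in the surgery and non-surgical arms. Naming the group with the larger count as surgery, and tossing a coin for a tie, is right with probability P(X_S > X_N) + 0.5 × P(X_S = X_N). An intact blind gives 0.50.

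**Step 1. Earlier rates taken as known (binomial counts).**

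| Surgery rate | Non-surgical rate | Right, 63 per arm | Right, 50 per arm |
|---|---|---|---|
| 12.5% (arm of 40) | 5% | 0.914 + 0.5 × 0.041 = 0.93 | 0.881 + 0.5 × 0.059 = 0.91 |
| 14.3% (arm of 35) | 5% | 0.96 | 0.95 |
| 11.1% (arm of 45) | 5% | 0.90 | 0.87 |

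**Step 2. Allowing for the small earlier trial.** The rates rest on seven events, and Fisher's exact test of 5/40 against 2/40 gives P = 0.43. With Jeffreys priors the rates follow Beta(5.5, 35.5) and Beta(2.5, 38.5), and the new counts are beta-binomial:

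- 63 per arm: 0.794 + 0.5 × 0.054 = 0.82.
- 50 per arm: 0.775 + 0.5 × 0.068 = 0.81.

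With an assumed earlier surgery arm of 45 or 35 in place of 40, the figure at 63 per arm is 0.78 or 0.86.

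**Step 3. A higher non-surgical rate (assumed), surgery rate 12.5%, 63 per arm.**

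- Non-surgical 7.5%: 0.82.
- Non-surgical 10%: 0.67.
- Non-surgical 12.5%: 0.50.

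**Step 4. Hardware removals not counted.** The earlier counts become 1 against 2. With 1/40 and 2/40 at 63 per arm, surgery has more events with probability 0.16, the same number 0.15, and fewer 0.69. The direction reverses. The SAP's account of the earlier trial does call hardware removal secondary surgery, but the Section 2 table does not define the term.

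**The case against.** The best defence is that efficacy is read first. The OMAS interval is compared with the margin for both scenarios, the sentences are closed options, and Section 2 can only leave the reading alone or add one caution. A guess about allocation cannot move a confidence interval. This stands, and it limits the harm. A reader might infer from the Section 3 statement that the efficacy consensus is formed unblinded. The documents do not support that: they show a possible guess made after the OMAS reading. The meeting flow chart is also not visible in the text at hand, so it may already mark a lock after Section 1.

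Second, the signal is weak evidence about the present trial. It comes from seven events and an assumed arm size. The SAP also reports that 40% of the 40 non-surgical patients had compromised healing and names loss of mortise congruence as the main worry without surgery, so members could expect operations in either arm. This stands too, and is why 93% should not be the headline.

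Third, the table pools all secondary operations without showing their type, and calling it most appropriate is a comparison with harms that are more revealing. Pooling does help. Even so, protection of the blind is the stated ground for the choice, and the plan's only cited comparable data do not support it.

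Fourth, direction matters for harms. The SAP's trial objectives make non-inferiority depend on no significantly increased risk of harms, and the caution has a higher/lower slot. That is a real cost of hiding direction. But the Section 2 question is only whether an imbalance exists, and the slot can be filled in Section 4.

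**Conclusion.** The concern holds in a limited form. Showing secondary surgery by coded group gives the committee a better-than-chance guess at allocation before the code is broken, so the blinding-preserving label is not supported by the plan's own evidence. The guess is right about 81% to 82% of the time if the present trial resembles the cited one, with its surgery arm assumed to be 40 and its small size allowed for. It is 93% if 12.5% and 5% are taken as known with 63 per arm, and 67% if the non-surgical rate is 10%. All of these rest on hardware removals being counted.

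What is exposed is the YES / NO judgement on imbalance and any rewording of the initial reading before Section 3. The OMAS reading itself is largely protected, and no breach of the blind is shown. This is a minor point, worth acting on because the remedy costs little.

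**What to change.** 1. Record and sign the Section 1 efficacy sentences for both scenarios as final before the Section 2 table is opened, and move the efficacy consensus statement from Section 3 to that point.
2. In Section 2 show only the unsigned absolute difference in secondary surgery and its P-value, and answer YES / NO on that. Enter the group counts and the higher/lower direction in Section 4 after unblinding, where the same sentence already stands.
3. Do not describe secondary surgery shown by coded group as blinding-preserving.

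The cost is a changed table shell and a changed meeting order; no analysis changes. The downside is that the committee sees the direction of the harm difference only after unblinding. Since the SAP bars changes to the interpretation at that stage, it should say that adding the counts and direction only completes the wording already agreed.
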